7. DISCONTINUATION OF STUDY INTERVENTION AND PARTICIPANT DISCONTINUATION/WITHDRAWAL

7.1. Discontinuation of Study Intervention

It may be necessary for a participant to permanently discontinue study intervention. Reasons for permanent discontinuation of study intervention include the following:

- AE requiring discontinuation in investigator's view.
- Pregnancy.

If study intervention is permanently discontinued, the participant will not remain in the study for further evaluation. See the [SoA](#) for data to be collected at the time of discontinuation of study intervention. In the event of discontinuation of study intervention, it must be documented on the appropriate CRF/in the medical records whether the participant is discontinuing further receipt of study intervention or also from study procedures, posttreatment study follow-up, and/or future collection of additional information.

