7.2. Participant Discontinuation/Withdrawal From the Study

A participant may withdraw from the study at any time at their own request. Reasons for discontinuation from the study include the following:

- Refused further study procedures;
- Lost to follow-up;
- Death;
- Study terminated by sponsor;
- Pregnancy;
- Behavioral, compliance, or administrative reasons.

At the time of discontinuing from the study, if possible, an early discontinuation visit should be conducted. See the [SoA](#) for assessments to be collected at the time of study discontinuation and follow-up and for any further evaluations that need to be completed.

The early discontinuation visit applies only to participants who are enrolled/randomized and then are prematurely withdrawn from the study. Participants should be questioned regarding their reason for withdrawal.

The participant will be permanently discontinued from the study intervention and the study at that time.

If a participant withdraws from the study, they may request destruction of any remaining samples taken and not tested, and the investigator must document any such requests in the site study records and notify the sponsor accordingly.

If the participant withdraws from the study and also withdraws consent (see Section 7.2.1) for disclosure of future information, no further evaluations will be performed and no additional data will be collected. The sponsor may retain and continue to use any data collected before such withdrawal of consent.

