7.2.1. Withdrawal of Consent

Participants who request to discontinue receipt of study intervention will remain in the study and must continue to be followed for protocol-specified follow-up procedures. The only exception to this is when a participant specifically withdraws consent for any further contact with them or persons previously authorized by the participant to provide this information. Participants should notify the investigator in writing of the decision to withdraw consent from future follow-up, whenever possible. The withdrawal of consent should be explained in detail in the medical records by the investigator, as to whether the withdrawal is only from further receipt of study intervention or also from study procedures and/or posttreatment study

follow-up, and entered on the appropriate CRF page. In the event that vital status (whether the participant is alive or dead) is being measured, publicly available information should be used to determine vital status only as appropriately directed in accordance with local law.

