8.4.1. Time Period and Frequency for Collecting AE and SAE Information

The time period for actively eliciting and collecting AEs and SAEs ("active collection period") for each participant begins from the time the participant provides informed consent, which is obtained before undergoing any study-related procedure and/or receiving study intervention), through and including a minimum of 28 calendar days after the last administration of the study intervention.

Follow-up by the investigator continues throughout the active collection period and until the AE or SAE or its sequelae resolve or stabilize at a level acceptable to the investigator.

When a clinically important AE remains ongoing at the end of the active collection period, follow-up by the investigator continues until the AE or SAE or its sequelae resolve or stabilize at a level acceptable to the investigator and Pfizer concurs with that assessment.

For participants who are screen failures, the active collection period ends when screen failure status is determined.

If the participant withdraws from the study and also withdraws consent for the collection of future information, the active collection period ends when consent is withdrawn.

If a participant permanently discontinues or temporarily discontinues study intervention because of an AE or SAE, the AE or SAE must be recorded on the CRF and the SAE reported using the CT SAE Report Form.

Investigators are not obligated to actively seek information on AEs or SAEs after the participant has concluded study participation. However, if the investigator learns of any SAE, including a death, at any time after a participant has completed the study, and they consider the event to be reasonably related to the study intervention, the investigator must promptly report the SAE to Pfizer using the CT SAE Report Form.

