8.4.3. Follow-Up of AEs and SAEs

After the initial AE or SAE report, the investigator is required to proactively follow each participant at subsequent visits/contacts. For each event, the investigator must pursue and obtain adequate information until resolution, stabilization, the event is otherwise explained, or the participant is lost to follow-up (as defined in [Section 7.3](#)).

In general, follow-up information will include a description of the event in sufficient detail to allow for a complete medical assessment of the case and independent determination of possible causality. Any information relevant to the event, such as concomitant medications and illnesses, must be provided. In the case of a participant death, a summary of available autopsy findings must be submitted as soon as possible to Pfizer Safety.

Further information on follow-up procedures is provided in [Appendix 3](#).

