8.4.5.1. Exposure During Pregnancy

An EDP occurs if:

- A female participant is found to be pregnant while receiving or after discontinuing study intervention until the follow-up visit (28-35 days after last dose of study drug).
- A male participant who is receiving or has discontinued study intervention inseminates a female partner until the follow-up visit (28-35 days after last dose of study drug) for the participant.
- A female nonparticipant is found to be pregnant while being exposed or having been exposed to study intervention because of environmental exposure. Below are examples of environmental EDP:
 - A female family member or healthcare provider reports that she is pregnant after having been exposed to the study intervention by ingestion, inhalation, or skin contact.
 - A male family member or healthcare provider who has been exposed to the study intervention by ingestion, inhalation, or skin contact then inseminates his female partner prior to or around the time of conception.

The investigator must report EDP to Pfizer Safety within 24 hours of the investigator's awareness, irrespective of whether an SAE has occurred. The initial information submitted should include the anticipated date of delivery (see below for information related to termination of pregnancy).

- If EDP occurs in a participant/participant's partner, the investigator must report this information to Pfizer Safety on the CT SAE Report Form and an EDP Supplemental Form, regardless of whether an SAE has occurred. Details of the pregnancy will be collected after the start of study intervention and until the follow-up visit (28-35 days after last dose of study drug) for the participant.

- If EDP occurs in the setting of environmental exposure, the investigator must report information to Pfizer Safety using the CT SAE Report Form and EDP Supplemental Form. Since the exposure information does not pertain to the participant enrolled in the study, the information is not recorded on a CRF; however, a copy of the completed CT SAE Report Form is maintained in the investigator site file.

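### Protocol 7.1 removes from the study anyone who permanently stops dosing; this contradicts 7.2.1 and leaves the 28-35 day adverse-event contact open to omission

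*Protocol*

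**What the plan says.** Protocol 7.1 names two reasons for permanently stopping study intervention: an AE that in the investigator's view requires it, and pregnancy. The list is introduced as inclusive, not exhaustive. The section then sets the consequence for any permanent stop: "If study intervention is permanently discontinued, the participant will not remain in the study for further evaluation". It next sends the site to the Schedule of Activities (SoA) for the data due when dosing is discontinued, and asks the site to record "whether the participant is discontinuing further receipt of study intervention or also from study procedures, posttreatment study follow-up".

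Protocol 7.2.1 says: "Participants who request to discontinue receipt of study intervention will remain in the study and must continue to be followed for protocol-specified follow-up procedures". Its sole exception is a participant who withdraws consent for further contact.

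Protocol 8.4.1 sets the active collection period for AEs and serious AEs for each participant, "through and including a minimum of 28 calendar days after the last administration of the study intervention". For an enrolled participant it gives one early end: when someone "withdraws from the study and also withdraws consent for the collection of future information, the active collection period ends when consent is withdrawn". The same section says that investigators need not actively look for events once the participant has finished taking part. After that point it requires prompt reporting only of serious events that the investigator happens to learn of and considers reasonably related.

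The SoA has an early termination column and a follow-up at 28 to 35 days after the final dose, which may be by telephone. SAP 3.5.1 counts events in follow-up, up to 28-35 days after the last dose, as treatment emergent and attributes them to the last treatment taken.

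**The concern.** Whether a participant who stops dosing stays under observation is an operative rule, and the protocol answers it in two ways. For someone who asks to stop, a site that obeys 7.1 disobeys 7.2.1, and the reverse.

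The matter reaches the primary endpoint because that endpoint is safety: treatment-emergent AEs, laboratory abnormalities, vital signs and ECGs. The SAP's treatment-emergent window assumes that someone asks about events up to 28-35 days after the last dose. If 7.1 is taken to end participation at the stop, a new event that begins after the early termination assessments may never be asked about. Those who stop because of an AE are among the people for whom this follow-up is wanted.

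**Working it through.** The protocol states no figure here to reproduce, so the check is a comparison of texts.

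1. **7.1 against 7.2.1.** The 7.1 rule attaches to permanent discontinuation as such. Because its list of reasons is open-ended, a stop at the participant's request falls under it. Section 7.2.1 addresses that same group and says they remain in the study and must be followed. One text removes them and the other keeps them. This is a direct contradiction, confined to participant-requested stops. For stops due to an AE, or under the QTcF limits in 7.1.1, section 7.2.1 is silent.

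2. **7.1 against 8.4.1.** The collection period covers each participant and runs at least 28 days past the last dose. Leaving the study does not shorten it; leaving and also withdrawing consent does. On this text alone, collection would continue for an early stopper. But 8.4.1 also ends the duty to seek events once participation has concluded, and it does not say when that is for someone removed under 7.1. Read with 7.1, the natural literal answer is the day of the stop. The two sections can be reconciled, but only if the site chooses the protective reading.

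3. **Whether other text closes the gap.**
   - Under 8.4.3, after an initial report "the investigator is required to proactively follow each participant at subsequent visits/contacts". That secures events already reported. It does not ensure that a new, late event is asked about.
   - The SoA pointer in 7.1 covers data at the time of discontinuation, not weeks later.
   - The follow-up rules for QTc prolongation (8.3.3), kidney injury (7.1.2) and liver injury (Appendix 6) act on findings already detected.

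4. **Texts that look contradictory but can be reconciled.**
   - Section 7.2 refers sites to the SoA "for assessments to be collected at the time of study discontinuation and follow-up and for any further evaluations that need to be completed", yet it also states that a withdrawn participant leaves both the intervention and the study. On leaving the study it agrees with 7.1.
   - Section 8.4.5.1 counts a pregnancy found "while receiving or after discontinuing study intervention until the follow-up visit (28-35 days after last dose of study drug". Its duties also extend to partners and other non-participants and run to the pregnancy outcome, so they do not depend on remaining in the study.
   - The recording requirement in 7.1 refers to discontinuation without the word permanent. It still has a use for temporary stops (7.1.3 allows them) and for stops at the participant's request.

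5. **What is exposed.** Under the literal reading, one scheduled contact per early stopper, at 28-35 days. It covers the time from the early termination assessments to the end of the 8.4.1 window.

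**The case against.** The strongest reply is that an ordinary reader would reconcile the sections: no more dosing and no more periods, then the early termination assessments, then safety follow-up. Section 8.4.1 is the specific rule for AE collection, and it separates leaving the study from ending collection. Section 7.2 shows that someone can leave the study and still have assessments. The SoA also points to 8.4.3 for follow-up of AEs. The 7.2.1 text stands under a heading on withdrawal of consent and concerns requested stops, while 7.1 names AEs and pregnancy, so the direct clash does not cover the stops that matter most for safety.

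Much of this stands. It limits the direct contradiction to one pair of sentences and shows that the intended conduct is probably the protective one. It does not remove the point. The protective reading is not what 7.1 says, the open-ended list brings requested stops under its rule, and the release in 8.4.1 gives a literal reader grounds to stop asking.

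A reader might go further and infer that 7.1 contradicts every section that mentions follow-up. The documents do not support that: 7.2 agrees that the participant leaves the study, and 8.4.5.1 and the recording requirement can be reconciled with 7.1.

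**Conclusion.** The 7.1 sentence is wrong as written: it is an unconditional operative rule that 7.2.1 contradicts and that weakens 8.4.1. Confidence in the wording conflict is high. The consequence is small and conditional: one contact at 28-35 days per early stopper, and only if a site applies 7.1 literally. Whether any site would do so is an assumption.

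It would be tempting to infer a material or informative loss on the primary safety endpoint. The documents do not support that. They give no expected number of early stops and no rate of late-onset events, so no number of lost events can be derived. Events already reported, and ECG, kidney and liver findings already detected, have their own follow-up rules. This is a minor correction, worth making because the endpoint is safety and the cost is close to nothing.

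**What to change.** Replace the 7.1 sentence with: *A participant who permanently discontinues study intervention will receive no further dosing or dosing periods, will complete the SoA early termination assessments, and will remain in safety follow-up through the 8.4.1 window, including the 28-35 day contact, unless consent is withdrawn.*

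Align 7.2 and 7.2.1 to this rule, so that every permanent stop, whatever its reason, leads to the same follow-up.

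The cost is protocol wording. The early termination assessments and the follow-up contact are already in the SoA, and the contact may be by telephone. No procedure is added, and the treatment-emergent window in SAP 3.5.1 needs no change.

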7.1.1. ECG Changes

A participant who meets either bulleted criteria based on the average of triplicate ECG readings will be withdrawn from the study intervention.

- QTcF >500 ms.
- Change from baseline: QTcF >60 ms.

If a clinically significant finding is identified (including, but not limited to, changes from baseline in QTcF after enrollment), the investigator or qualified designee will determine if the participant can continue in the study and if any change in participant management is needed. This review of the ECG printed at the time of collection must be documented. Any new clinically relevant finding should be reported as an AE.

7.1.2. Potential Cases of Acute Kidney Injury

Abnormal values in SCr concurrent with presence or absence of increase in BUN that meet the criteria below, in the absence of other causes of kidney injury, are considered potential cases of acute kidney injury and should be considered important medical events.

An increase of ≥ 0.3 mg/dL (or ≥ 26.5 μ mol/L) in SCr level relative to the participant's own baseline measurement should trigger another assessment of SCr as soon as practically feasible, preferably within 48 hours from awareness.

If the second assessment (after the first observations of ≥ 0.3 mg/dL [or ≥ 26.5 μ mol/L] in SCr relative to the participant's own baseline measurement) is ≥ 0.4 mg/dL (or ≥ 35.4 μ mol/L), the participant should be discontinued from the study and adequate, immediate, supportive measures taken to correct apparent acute kidney injury.

Participants should return to the investigator site and be evaluated as soon as possible, preferably within 48 hours from awareness of the second assessment confirming abnormal SCr result. This evaluation should include laboratory tests, detailed history, and physical assessment. In addition to repeating SCr, laboratory tests should include serum BUN, serum creatine kinase, and serum electrolytes (including at a minimum potassium, sodium, phosphate/phosphorus, and calcium), in addition to urinary dipstick, urine microscopic examination, and urinary indices. All cases confirmed on repeat testing as meeting the laboratory criteria for acute kidney injury, with no other cause(s) of laboratory abnormalities identified, should be considered potential cases of drug-induced kidney injury irrespective of availability of all the results of the investigations performed to determine etiology of the abnormal SCr. If ≥ 2 healthy participants in a given period are noted to have 2 *consecutive* SCr results of ≥ 0.3 mg/dL (or ≥ 26.5 μ mol/L), an assessment of whether the finding may be considered an adverse drug reaction should be undertaken.

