(diastolic), the BP should be repeated 2 more times and the average of the 3 BP values should be used to determine the participant's eligibility.

9. Standard 12-lead ECG that demonstrates clinically relevant abnormalities that may affect participant safety or interpretation of study results (eg, QTcF >450 ms, complete LBBB, signs of an acute or indeterminate- age myocardial infarction, ST-T interval changes suggestive of myocardial ischemia, second- or third- degree AV block, or serious bradyarrhythmias or tachyarrhythmias). If the uncorrected QT interval is >450 ms, this interval should be rate-corrected using the Fridericia method only and the resulting QTcF should be used for decision making and reporting. If QTcF exceeds 450 ms, or QRS exceeds 120 ms, the ECG should be repeated twice and the average of the 3 QTcF or QRS values used to determine the participant's eligibility. Computer-interpreted ECGs should be overread by a physician experienced in reading ECGs before excluding a participant.
10. Participants with **ANY** of the following abnormalities in clinical laboratory tests at screening, as assessed by the study-specific laboratory and confirmed by a single repeat test, if deemed necessary:
 - eGFR <60 mL/min/1.73m² based on CKD-EPI equation;
 - AST **or** ALT level $\geq 1.5 \times$ ULN;
 - Gamma-GT $>$ ULN;
 - Alkaline phosphatase $>$ ULN;
 - Total bilirubin level $\geq 1.5 \times$ ULN; participants with a history of Gilbert's syndrome may have direct bilirubin measured and would be eligible for this study provided the direct bilirubin level is \leq ULN.

Other Exclusion Criteria:

11. History of alcohol abuse or binge drinking and/or any other illicit drug use or dependence within 6 months of Screening. Binge drinking is defined as a pattern of 5 (male) and 4 (female) or more alcoholic drinks in about 2 hours. As a general rule, alcohol intake should not exceed 14 units per week (1 unit = 8 ounces (240 mL) beer, 1 ounce (30 mL) of 40% spirit, or 3 ounces (90 mL) of wine).
12. Blood donation (excluding plasma donations) of approximately 1 pint (500 mL) or more within 60 days prior to dosing.
13. History of sensitivity to sisunatovir or any of the formulation components.
14. Use of tobacco or nicotine-containing products in excess of the equivalent of 5 cigarettes/day or 2 chews of tobacco/day.

15. Unwilling or unable to comply with the criteria in the Lifestyle Considerations section of this protocol.

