10.7.2. Age-Specific Kidney Function Calculation Recommendations

10.7.2.1. Adults (18 Years and Above)—2021 CKD-EPI Equations

2021 CKD-EPI Scr Only	Scr (mg/dL)	Scys (mg/L)	Recommended eGFR Equation
Female	if ≤ 0.7	NA	$eGFR = 143 \times (Scr/0.7)^{-0.241} \times (0.9938)^{Age}$
Female	if > 0.7	NA	$eGFR = 143 \times (Scr/0.7)^{-1.200} \times (0.9938)^{Age}$
Male	if ≤ 0.9	NA	$eGFR = 142 \times (Scr/0.9)^{-0.302} \times (0.9938)^{Age}$
Male	if > 0.9	NA	$eGFR = 142 \times (Scr/0.9)^{-1.200} \times (0.9938)^{Age}$
2021 CKD-EPI Scr-Scys Combined	Scr (mg/dL)	Scys (mg/L)	Recommended eGFR Equation
Female	if ≤ 0.7	if ≤ 0.8	$eGFR = 130 \times (Scr/0.7)^{-0.219} \times (Scys/0.8)^{-0.323} \times (0.9961)^{Age}$
Female	if ≤ 0.7	if > 0.8	$eGFR = 130 \times (Scr/0.7)^{-0.219} \times (Scys/0.8)^{-0.778} \times (0.9961)^{Age}$
Female	if > 0.7	if ≤ 0.8	$eGFR = 130 \times (Scr/0.7)^{-0.544} \times (Scys/0.8)^{-0.323} \times (0.9961)^{Age}$
Female	if > 0.7	if > 0.8	$eGFR = 130 \times (Scr/0.7)^{-0.544} \times (Scys/0.8)^{-0.778} \times (0.9961)^{Age}$
Male	if ≤ 0.9	if ≤ 0.8	$eGFR = 135 \times (Scr/0.9)^{-0.144} \times (Scys/0.8)^{-0.323} \times (0.9961)^{Age}$
Male	if ≤ 0.9	if > 0.8	$eGFR = 135 \times (Scr/0.9)^{-0.144} \times (Scys/0.8)^{-0.778} \times (0.9961)^{Age}$
Male	if > 0.9	if ≤ 0.8	$eGFR = 135 \times (Scr/0.9)^{-0.544} \times (Scys/0.8)^{-0.323} \times (0.9961)^{Age}$
Male	if > 0.9	if > 0.8	$eGFR = 135 \times (Scr/0.9)^{-0.544} \times (Scys/0.8)^{-0.778} \times (0.9961)^{Age}$

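### The creatinine stopping rule in Section 7.1.2 is worded as an absolute value of 0.4 mg/dL, not a rise from baseline, so read literally the confirmatory repeat does no work

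*Protocol*

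**What the plan says.** Protocol Section 7.1.2 gives three serum creatinine (SCr) thresholds.

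- **Repeat trigger.** This one is explicitly relative: an increase of at least 0.3 mg/dL over the participant's "own baseline measurement should trigger another assessment of SCr as soon as practically feasible".
- **Individual stop.** The condition on the second assessment ends "own baseline measurement) is ≥ 0.4 mg/dL". The closing bracket belongs to an insertion that describes the first observation. If the condition is met, "the participant should be discontinued from the study and adequate, immediate, supportive measures taken".
- **Group trigger.** If two or more participants in a period have two consecutive "SCr results of ≥ 0.3 mg/dL", the possibility of an adverse drug reaction is to be assessed. The sentence mentions neither an increase nor a baseline.

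The adjacent ECG rule in Section 7.1.1 keeps level and change apart. It lists an absolute QTcF limit of 500 ms and, as a separate item, "Change from baseline: QTcF >60 ms". No other part of the protocol restates the 0.4 mg/dL stop or the 0.3 mg/dL group trigger as a change, and the SAP does not mention either.

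**The concern.** The repeat test exists to separate a confirmed rise from a transient one. It can do so only if the second result is judged against baseline. As the sentence is built, the second result is judged against 0.4 mg/dL itself, a level that nearly every healthy adult exceeds. Anyone who reaches the repeat would then be stopped, whatever it shows.

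This is an operative stopping rule in a cohort of about 12. Under Section 7.1, when study intervention is permanently discontinued, "the participant will not remain in the study for further evaluation". Sections 4.1 and 9.5 allow replacement only for non-safety discontinuations, so on its face a creatinine stop would not be replaced. The group trigger stops nobody, but if almost any two participants meet it, its prompt for an adverse drug reaction assessment carries no information.

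**Working it through.** **Inputs**

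- Thresholds: Section 7.1.2, as above.
- Age range: 18 to 65 years (Section 5.1).
- Renal eligibility: eGFR below 60 mL/min/1.73 m² is excluded, "based on CKD-EPI equation" (Section 5.2). There is no upper limit on eGFR and no lower limit on SCr.
- Equations: the rows headed "2021 CKD-EPI Scr Only" in Section 10.7.2.1.
- Assumptions: the baseline SCr values in step 4 are illustrative and not in the documents. The factor 88.4 is the standard unit conversion.

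**1. The plan's own paired units.** 0.3 × 88.4 = 26.5 μmol/L and 0.4 × 88.4 = 35.4 μmol/L. Both match Section 7.1.2, so the fault is not in the units.

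**2. What eGFR would escape the literal thresholds?** For SCr at or below 0.9 mg/dL in men and 0.7 mg/dL in women:

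- Men: eGFR = 142 × (SCr/0.9)^−0.302 × 0.9938^age
- Women: eGFR = 143 × (SCr/0.7)^−0.241 × 0.9938^age

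| SCr (mg/dL) | Men, 18 y | Men, 65 y | Women, 18 y | Women, 65 y |
|---|---|---|---|---|
| 0.4 (stop) | 162.2 | 121.1 | 146.3 | 109.2 |
| 0.3 (group trigger) | 176.9 | 132.1 | 156.8 | 117.1 |

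A participant avoids the literal threshold only with an eGFR above the tabulated value.

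**3. SCr at the entry limit.** Above those cut-points the exponent is −1.200. Solving for eGFR = 60:

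- Men: SCr = 0.9 × (142 × 0.9938^age / 60)^(1/1.2) = 1.68 mg/dL (18 y) to 1.32 mg/dL (65 y)
- Women: SCr = 0.7 × (143 × 0.9938^age / 60)^(1/1.2) = 1.31 mg/dL (18 y) to 1.03 mg/dL (65 y)

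At eGFR 90 the same equations give 0.94 to 1.20 mg/dL in men and 0.74 to 0.94 mg/dL in women, about two to three times the literal stop.

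**4. Literal against intended stop.** Repeat trigger = baseline + 0.3; intended stop = baseline + 0.4; literal stop = 0.4 throughout (all mg/dL).

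| Baseline | First value that triggers a repeat | Literal stop | Intended stop | Repeat values on which the readings disagree |
|---|---|---|---|---|
| 0.6 | 0.9 | 0.4 | 1.0 | 0.4 to just below 1.0 |
| 0.9 | 1.2 | 0.4 | 1.3 | 0.4 to just below 1.3 |
| 1.2 | 1.5 | 0.4 | 1.6 | 0.4 to just below 1.6 |

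In every row a repeat fully back at baseline meets the literal stop but not the intended one.

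**5. Cost of one needless stop.** The food-effect model in Section 9.3.3 uses only Treatments A (fed) and D (fasted), each planned for all 12 participants of Cohort 1. A stop before both are complete loses 1/12 = 8.3% of the pairs. This is conditional on a first rise of at least 0.3 mg/dL and on literal application; the documents give no frequency for either.

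**The case against.** The strongest reply is that nobody would read the rule this way. The preceding paragraph defines the trigger as a rise from baseline. The stopping sentence then recalls that trigger in shortened form, and 0.4 mg/dL reads as the next step on the same scale. Section 7.1.2 goes on to describe the second assessment as confirming an abnormal result, and the stated action is to correct apparent kidney injury; a repeat back at baseline confirms nothing. The group sentence follows text on confirmed cases and reuses the 0.3 mg/dL figure. Section 10.7.1 also speaks of a confirmed increase after baseline. The verb is *should*, which leaves room for judgement, and the harm requires a chain of unlikely events.

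Much of this stands. It shows what was intended, and it makes literal application improbable. It also keeps the point modest: the error runs toward over-stopping, and the 8.3% is not an expected loss. That a stop made on misapplied wording would not be replaced is an inference, because Section 9.5 does not address that case.

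It does not make the wording right. Section 10.7.1 supplies the frame of a rise from baseline but not the thresholds. Section 8.1 rules out protocol waivers and requires adherence to the study design, so a site should not have to depart from the text to apply a stopping rule sensibly.

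**Conclusion.** The concern holds: the stopping threshold and the group trigger are wrong as written. Read literally, the stop is met by any repeat of 0.4 mg/dL or more. On the protocol's equations that covers every participant except those with an eGFR above about 121 to 162 (men) or 109 to 146 (women), so the repeat does not separate transient from confirmed rises. The group trigger is met by almost any two participants.

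This conclusion rests on the grammar of two sentences and on the protocol's own equations; the illustrative baselines affect only the worked examples. The practical risk is conditional over-stopping, at up to one fed/fasted pair in 12 for each needless stop. Sample size and planned analyses are unaffected. It should be corrected because it is an operative stopping rule and the correction is small.

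**What to change.** Change two phrases in Section 7.1.2.

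- **Stopping sentence:** after the bracket, write *is an increase of ≥0.4 mg/dL (or ≥35.4 μmol/L) from the participant's own baseline*.
- **Group sentence:** write *2 consecutive SCr increases of ≥0.3 mg/dL (or ≥26.5 μmol/L) from baseline*.

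A repeat less than 0.4 mg/dL above baseline then does not stop the participant, and a repeat at or beyond that rise does. Each of the two consecutive results counts toward the group trigger only if it is at least 0.3 mg/dL above baseline. The cost is the two wording changes; no new sampling, analysis or SAP change is needed.
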